10.3.2.6. Adverse Events by Maximum Severity Grade Level

Treatment-emergent adverse events will be summarized by maximum CTCAE grade level of each preferred term. Each preferred term will be assigned to a grade level based on severity and seriousness, adapted from CTCAE Version 4.03 for grading severity of adverse events.

All serious adverse events will be categorized according to Grade definition.

If a patient has a non-serious adverse event with unknown grade, then the patient will be counted in the severity grade level category of "unknown," even if the patient has another occurrence of the same event with a grade present.

10.3.2.7. Adverse Events by Maximum Relationship

Treatment-emergent adverse events also will be summarized by maximum relationship of each preferred term to study drug (AVXS-101), as assessed by the investigator. If a patient has an adverse event with unknown relationship, then the patient will be counted in the relationship category of "unknown," even if the patient has another occurrence of the same event with a relationship present. The only exception is if the patient has another occurrence of the same adverse event with a relationship assessment of "possibly related" or higher. In this case, the patient will be counted under the "related" category.

10.4. Laboratory Evaluations

10.4.1. Analysis of Laboratory Data

Safety laboratory data and genetic diagnosis laboratory data generated by Q2, the designated central laboratory, will be used in all analyses for genetic diagnosis. Also, safety laboratory data generated by local lab will be used for safety analysis. Immunoassay data generated by CTL will be used in all analyses.

10.4.2. Variables and Criteria Defining Abnormality

Hematology variables include: hematocrit, hemoglobin, red blood cell (RBC) count, white blood cell (WBC) count, lymphocytes, neutrophils, lymphocytes, monocytes, eosinophils, basophils, bands, mean corpuscular volume (MCV), mean corpuscular hemoglobin (MCH), mean cell hemoglobin concentration (MCHC), and red cell distribution width (RDW).

Chemistry variables include: albumin, alanine aminotransferase (ALT/SGPT), alkaline phosphatase, aspartate aminotransferase (AST/SGOT), blood urea nitrogen (BUN), creatinine, gamma glutamyl transferase (GGT), glucose, serum total bilirubin, direct bilirubin, total creatine kinase (CK), CK-MB, and electrolytes.

Urinalysis variables include: specific gravity, pH, ketones, glucose, protein, blood, leukocyte esterase, nitrites, bilirubin, red blood cell (RBC) count, white blood cell (WBC) count, yeast, squamous epithelial cells, casts, crystals, bacteria.

Immunology variables include: mother's serum binding antibody titer to AAV9, serum binding antibody titer to AAV9, binding antibody titer to SMN, T-cell response to AAV9 and SMN.

The Criteria for PCS Laboratory Findings are maintained outside of this SAP.

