12.1.10.1. Hematology

Hematology analysis will include a complete blood count with differential and platelet count with smear. Samples will be collected and shipped in accordance with the laboratory manual provided by the central laboratory. Blood samples for hematology analysis will be collected as specified in the SoA ([Appendix 1](#)).

Immediate/same-day hematology analyses required during in-patient dosing, as determined by Investigator, will be performed as per investigational site standard procedures at the local laboratory. Investigators will receive hematology results from all trial visits from the central laboratory.

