12.1.10.2. Blood Chemistry

Samples will be collected and shipped in accordance with the laboratory manual provided by the central laboratory. Blood samples for chemistry analysis will be collected as specified in the SoA ([Appendix 1](#)).

Immediate/same-day chemistry analyses required during in-patient dosing, as determined by Investigator, will be performed as per investigational site standard procedures at the local laboratory.

Chemistry analysis will include the following at all trial visits:

- Serum GGT
- AST/ALT
- Serum total bilirubin
- Direct bilirubin
- Albumin
- Glucose
- Creatinine kinase
- Creatinine
- BUN
- Electrolytes
- Alkaline phosphatase

CK-MB or Troponin I will be collected as specified in the SoA ([Appendix 1](#)) as applicable:

- Patients screened and dosed before IRB/EC approval of Protocol version 3.0 incorporating Amendment 2 will be tested for CK-MB throughout the study.
- Patients screened before IRB/EC approval of Protocol version 3.0 incorporating Amendment 2 but dosed afterwards will be tested for CK-MB at screening but for Troponin 1 at baseline and thereafter.
- Patients screened after IRB/EC approval of Protocol version 3.0 incorporating Amendment 2 will be tested for Troponin 1 from screening onwards.

Investigators will receive chemistry results from all trial visits from the central laboratory.

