10.3.2.4. Adverse Events of Special Interest

The following specific treatment-emergent adverse events of special interest, which may be searched using Standardized MedDRA queries, will be summarized:

- Hepatotoxicity, identified via the following SMQs:
 - Hepatic failure, fibrosis and cirrhosis and other liver damage-related conditions (SMQ)
 - Hepatic disorders (SMQ)
- Thrombocytopenia, identified via the following SMQs/HLT:
 - Hematopoietic thrombocytopenia (SMQ)
 - Haemorrhages (SMQ)
 - All TEAEs which code into the "Platelet disorders NEC" HLT
- Cardiac events, identified via the following SMQs:
 - Ischemic heart disease (SMQ)
 - Cardiomyopathy (SMQ)
 - Cardiac arrhythmias (SMQ)
 - Embolic and thrombotic events (SMQ)
 - Myocardial infarction (SMQ)
- Ganglionitis, with potential cases identified by reviewing all TEAEs which code to the "Nervous System Disorders" SOC

For each AE of interest category, the number and percentage of patients experiencing at least one TEAE in the search for the event of interest will be presented overall. AEs of special interest will be summarized by SOC and PT overall.

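### The SAP laboratory lists omit platelet count and troponin I, and the thrombocytopenia AESI has no pre-specified graded laboratory display

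*SAP*

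**What the plan says.** **Collection.** Protocol 12.1.10.1 states: "Hematology analysis will include a complete blood count with differential and platelet count with smear". Protocol 12.1.10.2 states: "CK-MB or Troponin I will be collected as specified in the SoA". It then assigns the cardiac marker by date relative to approval of protocol version 3.0. Patients screened after approval "will be tested for Troponin 1 from screening onwards". SAP Table 1 carries the same either/or row.

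**Laboratory variables in the SAP.** SAP 10.4.2 opens: "Hematology variables include: hematocrit, hemoglobin, red blood cell (RBC) count, white blood cell (WBC) count, lymphocytes, neutrophils, lymphocytes, monocytes". That list closes with "mean cell hemoglobin concentration (MCHC), and red cell distribution width (RDW". Platelet count is not in it, and lymphocytes appears twice. The chemistry list ends: "serum total bilirubin, direct bilirubin, total creatine kinase (CK), CK-MB, and electrolytes". Troponin I is not in it. The same section says that the PCS criteria are kept in a separate document.

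**AESIs.** Protocol 13.1.3 names four: hepatotoxicity, thrombocytopenia, cardiac events and sensory abnormalities suggestive of ganglionopathy. SAP 10.3.2.4 finds them by searching coded adverse event terms, for example "Thrombocytopenia, identified via the following SMQs/HLT".

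**Laboratory output.** SAP 10.4.3 plans by-visit summaries, mean changes for every parameter the protocol specifies, shift tables, PCS counts, CTCAE-grade tables for a named set of tests, and listings.

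**The concern.** Thrombocytopenia and cardiac events are two safety signals that the sponsor singled out for 24-hour reporting. Each has a blood test that the trial collects, and neither test is fully named where the SAP lists its laboratory variables. A programmer working from 10.4.2 could leave out platelets and produce cardiac-marker tables from CK-MB alone, although many patients may never have had CK-MB measured after dosing.

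What is at stake is whether an asymptomatic platelet fall, not reported as an adverse event, would be visible by severity in a pre-specified table. With about 30 patients, a mean change can hide a deep but short-lived fall in a few infants. Counts by worst grade would show it.

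**Working it through.** No sample size, power or error rate is involved, so nothing needs calculating. The check sets the sections side by side.

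**1. Is each test collected, and is it named?**

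| Test | Protocol 12.1.10 | SAP Table 1 | SAP 10.4.2 |
|---|---|---|---|
| Platelet count | Yes, with hematology | Within the hematology row | Not named |
| CK-MB | Yes, by date group | Named | Named |
| Troponin I | Yes, by date group | Named | Not named |

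**2. Which patients have which cardiac marker?** Protocol 12.1.10.2 and the footnotes to protocol Table 3 give three groups relative to approval of version 3.0:

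- Screened and dosed before: CK-MB throughout.
- Screened before, dosed after: CK-MB at screening, troponin I from baseline.
- Screened after: troponin I from screening.

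For the second group, a CK-MB summary has a screening value and no scheduled post-dose value. For the third it has no scheduled value at all. CK-MB, the only one of the two alternative markers that 10.4.2 names, therefore gives a change from baseline only in the first group. The documents do not give the group sizes. Protocol Table 3 and the schedule show no cardiac-marker sample between screening and Day 7, so the second group's baseline troponin I rests on the text of 12.1.10.2 and should be confirmed in the data.

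**3. Which outputs in SAP 10.4.3 reach platelets and troponin I?**

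| Output | How its scope is set | Platelets | Troponin I |
|---|---|---|---|
| By-visit summary | Laboratory tests in general | Can be included | Can be included |
| Mean change | Every protocol-specified parameter | Covered | Covered |
| Shift tables | Laboratory values, no tests named | Not assured | Not assured |
| PCS counts | Separate document | Cannot be checked | Cannot be checked |
| CTCAE-grade tables | Named set: hemoglobin, ALT, AST, alkaline phosphatase, total bilirubin | Excluded | Excluded |
| Hematology listing | Patients with abnormal hemoglobin | Only if hemoglobin is also abnormal | Not applicable |

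**4. Comparison with another AESI.** Hepatotoxicity has grade tables, listings for Grade 3 or higher, and 21 threshold rows combining ALT or AST with bilirubin (8 + 6 single-enzyme rows and 3 + 4 joint rows). Thrombocytopenia has no graded or threshold row named in the SAP.

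**5. Other cardiac evidence.** SAP 10.6 and 10.7 plan ECG changes from baseline, a listing of ECGs that the central reviewer flags as PCS, and centrally assessed Holter time points. SAP 10.10 plans echocardiogram change from baseline and sends the data for central review. None of this depends on reported adverse event terms.

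**The case against.** The best reply is that the omission has little consequence. The 10.4.2 lists are introduced by a verb that does not make them exhaustive. Nothing in 10.4.3 says that its tables are built from those lists. Mean changes, with minimum and maximum, are promised for every protocol-specified parameter, which covers both tests. SAP 4.6.4 also mentions cardiac enzymes in general. Asymptomatic laboratory changes can be recorded as Grade 1 adverse events, AESIs are collected whatever their grade, and DSMB reports include clinically significant laboratory results. Finally, the SAP grades a selected set of tests and also leaves out white cells, neutrophils, GGT and creatinine. No protocol section requires a graded platelet table.

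Most of this stands, and it rules out two stronger readings. A reader might infer that platelet falls or troponin rises would appear in no shift or abnormality table. The documents do not say so: the shift tables are not tied to 10.4.2, and the PCS criteria are not available to check. A reader might also infer that both AESIs rest on investigator-reported terms alone. That is wrong for the cardiac AESI, given the ECG, Holter and echocardiogram analyses. It is not established for platelets either, which are covered at least by the mean-change summary.

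The reply does not remove the gap in graded output. The grade tables carry their own closed list, so the open wording of 10.4.2 does not bring platelets into them. Nor does it supply a rule for presenting two cardiac markers measured in different patients.

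**Conclusion.** The point holds in a limited form. SAP 10.4.2 is out of line with the protocol and with SAP Table 1 for two tests, each relevant to one of the four AESIs. For thrombocytopenia the consequence is concrete: as written, the plan pre-specifies no graded laboratory display, and a patient with low platelets and normal hemoglobin would not enter the hematology listing. For the cardiac AESI the consequence is smaller. The missing name and the missing presentation rule make the marker summaries ambiguous, but other objective cardiac data are analyzed.

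The effect on results cannot be sized, because the documents give neither the number of patients per cardiac marker nor the content of the PCS criteria. If those criteria already include platelets and troponin I, the gap narrows to the grade tables, the listing trigger and the two-marker rule. A drafting lapse is the likely explanation: SAP section 2 still refers to protocol version 2.1, while troponin I is tied to version 3.0. The correction is worth making before the safety tables are produced, because it concerns a designated signal and costs little.

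**What to change.** In SAP 10.4.3:

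- Add platelet count to the CTCAE-grade tables, by maximum post-baseline grade as for hemoglobin.
- Make low platelets a trigger for the hematology listing alongside abnormal hemoglobin.
- Name platelet count and troponin I in the shift and PCS outputs, and confirm that the separate PCS document covers both.
- Summarize CK-MB and troponin I separately, each with its own denominator. Report change from baseline only for patients whose baseline and post-dose values are the same marker.

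In SAP 10.4.2, add platelet count and troponin I to the lists and delete the repeated lymphocytes entry.

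The cost is a few table rows and one listing condition, using data already collected. No visit, sample, dose or clinical rule changes, and the primary and secondary efficacy analyses are unaffected.

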10.4.3. Statistical Methods

Clinical laboratory test will be summarized at each visit during the treatment period. The baseline value will be the last measurement on or before the day of the infusion of study drug. This same baseline value will be used for all changes from baseline tables in the treatment period and post-treatment period. Natural history control data is not available for this evaluation.

Mean changes from baseline to End of Study/Early Termination will be summarized for each protocol-specified laboratory parameter with the baseline mean, visit mean, change from baseline mean, standard deviation, minimum, maximum, and median.

During the treatment period, laboratory data values will be categorized as low, normal, or high based on normal ranges of the laboratory used in this study. Shift tables from baseline to minimum value, maximum value, and final values during the treatment period will be created. The shift tables will cross tabulate the frequency of patients with baseline values below/within/above the normal range versus minimum/maximum/final values below/within/above the normal range.

The number and percentage of patients with post-baseline values during the treatment period meeting the specified criteria for Potentially Clinically Significant (PCS) laboratory values will be summarized. A post-baseline value must be more extreme than the baseline value to be considered a PCS finding. A listing will be provided that presents all of the lab values for the patients meeting PCS criteria during treatment Period.

For hemoglobin and the liver function tests (LFTs) of ALT, AST, alkaline phosphatase, and total bilirubin, the number and percentage of patients in each treatment group with a maximum CTCAE Grade of 1, 2, 3, or 4 (as defined by the central laboratory and based on CTCAE v4.03) at any post-baseline visit (regardless of the baseline value) through the end of treatment (i.e., Final Treatment Value) will be summarized. All LFT tables will include summary rows for the number and percentage of patients with at least Grade 2 and at least Grade 3 laboratory abnormalities. The hemoglobin table will include a summary row for the number and percentage of patients with at least a Grade 2 laboratory abnormality. Listings of all ALT, AST, total, indirect and direct bilirubin, and alkaline phosphatase will be created for any patients who had at least a Grade 3 ALT, AST, alkaline phosphatase, or total bilirubin. A listing of hematology results will be provided for patients with hemoglobin abnormalities.

For patients with a Grade 3 or higher total bilirubin elevation, a listing of treatment-emergent adverse events (defined as preferred terms within the "Cholestasis and jaundice of hepatic origin" (broad search) SMQ, excluding preferred terms within the "Investigations" SOC) will be provided.

The number and percentage of patients meeting the following criteria will be summarized overall.

- ALT \geq 3x ULN with bilirubin < 2x ULN
- AST \geq 3x ULN with bilirubin < 2x ULN
- ALT \geq 5x ULN with bilirubin < 2x ULN
- AST \geq 5x ULN with bilirubin < 2x ULN
- ALT \geq 10x ULN with bilirubin < 2x ULN

- $AST \geq 10x$ ULN with bilirubin $< 2x$ ULN
- $ALT \geq 20x$ ULN with bilirubin $< 2x$ ULN
- $AST \geq 20x$ ULN with bilirubin $< 2x$ ULN
- $ALT \geq 3x$ ULN with bilirubin $\geq 2x$ ULN
- $AST \geq 3x$ ULN with bilirubin $\geq 2x$ ULN
- $ALT \geq 5x$ ULN with bilirubin $\geq 2x$ ULN
- $AST \geq 5x$ ULN with bilirubin $\geq 2x$ ULN
- $ALT \geq 10x$ ULN with bilirubin $\geq 2x$ ULN
- $AST \geq 10x$ ULN with bilirubin $\geq 2x$ ULN
- ALT and $AST \geq 3x$ ULN with bilirubin $< 2x$ ULN
- ALT and $AST \geq 5x$ ULN with bilirubin $< 2x$ ULN
- ALT and $AST \geq 10x$ ULN with bilirubin $< 2x$ ULN
- ALT and $AST \geq 3x$ ULN with bilirubin $\geq 2x$ ULN
- ALT and $AST \geq 5x$ ULN with bilirubin $\geq 2x$ ULN
- ALT and $AST \geq 10x$ ULN with bilirubin $\geq 2x$ ULN
- ALT and $AST \geq 20x$ ULN with bilirubin $\geq 2x$ ULN

A patient or event will be counted if the post-baseline laboratory values meet the above criteria regardless of the baseline laboratory value (i.e., the post-baseline laboratory value does not need to be worse than the baseline laboratory value). For patients meeting any elevation criterion, a corresponding listing of all ALT, AST, alkaline phosphatase, and total, direct, and indirect bilirubin values will be provided.

10.4.4. Drug-Induced Liver Injury

Drug-induced liver injury (DILI) has been the most frequent single cause of safety-related drug marketing withdrawals and as such with this pediatric population (SMA patients) and unique intervention (gene therapy), Sponsor took care to assess hepatic test results as drugs can cause liver injuries by many different mechanisms. Severe DILI cases rarely have been seen in drug development programs of significantly hepatotoxic drugs that do cause such injury. Evidence of hepatocellular injury is thus a necessary, but not sufficient, signal of the potential to cause severe DILI (note, however, that the drugs causing hepatic injury through mitochondrial toxicity may not cause early hepatotoxicity).

It is possible that although a drug may not cause severe liver injury, it could still result in laboratory evidence of mild, transient hepatic injury, with leakage of liver enzymes and the appearance in serum of elevations in aminotransferase activities to levels of 3, 5, and sometimes greater than 5 times the upper limits of normal (ULN). The liver enzyme data was evaluated according to these criteria and according to Hy's Law.

A finding of ALT elevation, usually substantial, seen concurrently with bilirubin $>2x$ ULN, identifies a drug likely to cause severe DILI (fatal or requiring transplant) at a rate roughly 1/10

the rate of Hy's Law cases. It is critical to rule out other causes of injury (e.g., other drugs or viral hepatitis) and to rule out an obstructive basis for the elevated bilirubin, so that alkaline phosphatase (ALP) should not be substantially elevated. In all cases to date, the small number of Hy's Law cases has arisen on a background of an increased incidence of more modest signs of hepatocellular injury (e.g., greater incidence of 3xULN elevations in AT than seen in a control group).

Briefly, Hy's Law cases have the following two components:

1. Subjects showing ALT or AST elevations, greater than 3xULN, combined with serum TBL to ≥ 2 xULN, without initial findings of cholestasis (elevated serum ALP);
2. No other reason can be found to explain the combination of increased ALT or AST and TBL, such as viral hepatitis A, B, or C, pre-existing or acute liver disease, or another drug capable of causing the observed injury.

For patients enrolled in this study these criteria are assessed in order to determine both general liver function enzyme changes (LFEs) according to change from baseline and over course of study. In addition, the assessment of changes in ALT or AST relative to TBL allowed assessment if a signal related to DILI occurred in any individual or group of patients.

10.5. Vital Signs

Vital signs (pulse, respiration, temperature, diastolic blood pressure, body weight, systolic blood pressure, pulse oximetry) will be examined at each visit. Clinically-significant, treatment-emergent findings will be reported as adverse events.

A summary of changes from first recorded value in vital signs will be described at each visit on the safety set. In addition, vital signs results will be flagged as Potentially Clinically Significant (PCS) if they meet the pre-specified criteria. The number and percent of patients meeting each PCS criterion will be summarized starting at Day 1 and continuing through the end of study.

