14.3. Efficacy Analysis

14.3.1. General Considerations

This trial will compare the activity of AVXS-101 administered IV versus the natural observational results from PNCR [24] in terms of sitting without support and survival rate.

The analysis of the primary and secondary efficacy endpoints will be performed for the ITT population, and efficacy completers populations. The analysis based on the ITT population will be considered as the primary analysis.

Unless otherwise specified, the baseline measurement is defined as the last non-missing measurement collected prior to or on the day of gene replacement therapy infusion (i.e., on or before Day 1 visit).

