1.2. Glossary of Definitions

Abbreviations list pertains to the SAP only.

| Abbreviation | Description |
|-----------------|--|
| AE | Adverse Event: Any untoward medical occurrence in a clinical investigation subject which does not necessarily have a causal relationship with the drug or device under study. |
| Age | For a given event, age will be expressed in months and rounded to one decimal place. A month is standardized to a period of 30 days. Age at Event = (Date of Event – Date of Birth + 1)/ 30. Age at Dosing = (Date of Gene Therapy Infusion – Date of Birth + 1)/ 30. |
| Baseline | Baseline, e.g., in terms of baseline laboratory values, vital signs, or physical exam results, refers to a measurement or evaluation made prior to initiation of gene therapy infusion. If there are multiple measurements prior to the initiation of gene therapy infusion, only the latest measurement will be considered as baseline for analysis purposes. |
| BiPAP | Bilevel Positive Airway Pressure, a form of non-invasive mechanical pressure support ventilation. |

| Abbreviation | Description |
|------------------------------|---|
| CHOP-INTEND | Children’s Hospital of Philadelphia Infant Test of Neuromuscular Disorders, a 16-item motor function assessment validated for use in infants with spinal muscular atrophy. |
| Day 1 | The day of the gene therapy treatment. |
| Dose | Total vector genome administrated (in vg /patient weight on Day – 1(kg)). |
| MedDRA | Medical Dictionary for Regulatory Activities is a medical terminology used to classify adverse event information associated with the use of biopharmaceuticals and other medical products. |
| CTCAE | Common Terminology Criteria for Adverse Events version 4.03. The CTCAE is descriptive terminology, involving a severity scale, which is used for AE reporting in particular for unique patient populations. It is a subset of MedDRA terminology. |
| Permanent Ventilation | Requirement of ≥ 16 -hour respiratory assistance per day (includes BiPAP) continuously for ≥ 14 days in the absence of an acute reversible illness, excluding perioperative ventilation. |
| PNCR | Pediatric Neuromuscular Clinical Research Network |
| Study Day | For any event of interest, Study Day = calendar date of event – calendar date of gene transfer +1. Day 1 is the Study Day of the gene transfer and any events occurring on the same calendar day as the gene transfer. |

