6.2. Key Definitions

6.2.1. Definition of Baseline

The baseline value refers to the last non-missing measurement collected before gene therapy infusion of study drug. On Study Day 1, all assessments should be performed prior to administering the gene therapy infusion of study drug per protocol. The baseline value is therefore determined by the last non-missing measurement collected on or before the first day of study drug administration. If multiple measurements are recorded on the same day, the last measurement recorded prior to the gene therapy infusion will be used as the baseline value. If these multiple measurements occur at the same time or time is not available, then the average of these measurements (for continuous data) or the worst among these measurements (for categorical data) will be considered as the baseline value. This same baseline value will be used for the treatment and post-treatment periods.

The baseline values will be the first non-missing values collected for the control patients from the PNCR dataset.

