Due to COVID-19 pandemic, a few patients may complete the final visit (18 months of age) months outside of protocol-defined visit window. Summary tables for efficacy analysis will be created based on the visits up to month 18 of age and any data collected after month 18 of age visit to the end of study visit will be grouped into “Month 19 of age and older. Data collected through the final visit will be presented in the listings. In case, multiple record falls within “Month 19 of age and older” visit then first record will be used for analysis.

Safety data, such as laboratory results, vital signs, ECGs, and physical exams will be assessed by date and study day. For lab data collected on an unscheduled visit, the protocol defined visit windows will be applied. For change from baseline analyses the value associated with the scheduled visit will be used. Due to the visit window (± 7 days) for Day 60 visit and Day 72

visit, there is an overlap when assigning data to these two visits. Data collected between Day 53 to Day 66 will be assigned to Day 60 visit. Data collected between Day 67 to Day 79 will be assigned to Day 72 visit. For summaries of shifts from baseline and potentially significant values, all post baseline values will be considered for these analyses. Baseline for safety measures will be defined as the latest value before Day 1.

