10.6. ECG

10.6.1. Additional Safety Endpoint: Cardiovascular Safety Evaluations

Serial ECG data will be collected at scheduled time points and provided in an external dataset. A 12-lead ECG will also be conducted at scheduled visits. The baseline value will be latest measure prior to dosing. Mean changes from baseline, standard deviation, minimum, maximum, and median to End of Study/Early Termination visit will be summarized for HR, PR, QR, QRS, QTcF.

The central reviewer will identify abnormal ECGs that are PCS, the definitions for which are maintained outside of this document.

A listing of all PCS ECGs will be provided. Summaries of ECG data will be presented overall.

10.7. 12-Lead Holter Monitor

A Holter monitor will continuously record the patient's 12-lead ECG for a total of 72 hours from Day -1 (24 hours prior to the start of gene replacement therapy infusion) through 48 hours after the start of infusion. On Days -1 to Day 3, serial ECG data will be pulled from the Holter monitor at time points of 'pre-dose', '2 hour', '4 hour', '6 hour', '8 hour', '12 hour', '24 hour',

'36 hour' and '48 hour' post-dose and assessed by a central reviewer. The summaries of Holter monitor data will be done by the actual treatment received overall.

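### SAP 10.5 measures vital-sign change from the first recorded (screening) value, contrary to the SAP's own last-pre-dose baseline, so 2 to 30 pre-dose days are counted as post-dose change

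*SAP*

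**What the plan says.** SAP 10.5 covers pulse, respiration, temperature, systolic and diastolic blood pressure, body weight and pulse oximetry. Its rule for change is: "A summary of changes from first recorded value in vital signs will be described at each visit on the safety set".

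Three other places in the SAP set a baseline that reaches vital signs:

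- SAP 1.2 defines the term with vital signs as a named example ("Baseline, e.g., in terms of baseline laboratory values, vital signs, or physical exam results"). Where several pre-infusion values exist, "only the latest measurement will be considered as baseline for analysis purposes".
- SAP 6.2.1, the general rule, provides that for several values on one day "the last measurement recorded prior to the gene therapy infusion will be used as the baseline value".
- SAP 6.4.1, in a paragraph that lists vital signs among the safety data, says: "Baseline for safety measures will be defined as the latest value before Day 1".

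The ECG rule in SAP 10.6.1 follows the same principle: "The baseline value will be latest measure prior to dosing". The SAP gives no reason for treating vital signs differently, and SAP 13 does not list this as a change from the protocol.

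**The concern.** The trial has a single arm, so the pre-dose reference is the only thing that separates change after infusion from growth, illness or disease progression already under way. If the reference is the screening value, whatever happened between screening and infusion is reported as change after treatment. The proportion is largest at the first visits after dosing, which is where an infusion-related shift in pulse, blood pressure or saturation would be looked for.

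There is also a reproducibility problem. The SAP does not say which section prevails, so two programmers could each follow it and produce different vital-sign tables.

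**Working it through.** The plan states no figure to reproduce. The check compares the rules and then counts days.

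**Which value each rule selects.** Vital signs, weight and length are scheduled at screening, Day -1 and Day 1 (SAP Table 1). Protocol 12.1.3 requires a pre-dose recording of vital signs and a pre-dose weight on Day 1. For a patient with all three:

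- SAP 10.5 selects the screening value.
- SAP 6.4.1, read literally, selects Day -1.
- SAP 1.2 and 6.2.1 select the Day 1 pre-dose value.

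**Length of the pre-dose span.** Screening runs from Day -30 to Day -2 (Protocol 7.1, SAP 3.5). On nominal protocol days with no Day 0, screening to Day 1 is 30 days at most and 2 days at least. From Day -1 to Day 1 is 1 day. From the Day 1 pre-dose value it is 0 days.

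**Share of the change interval that is pre-dose.** With g the days from screening to Day 1 and v the visit day, share = g / (g + v - 1).

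| Visit | Post-dose days (v - 1) | Screened Day -30 (g = 30) | Screened Day -2 (g = 2) |
|---|---|---|---|
| Day 2 | 1 | 30/31 = 97% | 2/3 = 67% |
| Day 7 | 6 | 30/36 = 83% | 2/8 = 25% |
| Day 30 | 29 | 30/59 = 51% | 2/31 = 6.5% |
| Day 90 | 89 | 30/119 = 25% | 2/91 = 2.2% |
| Day 180 | 179 | 30/209 = 14% | 2/181 = 1.1% |

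**Illustration with assumed values.** The entry criteria tolerate a fall in saturation of less than 4 percentage points between screening and dosing. Take 99 at screening, 97 on Day -1, 96 before dosing on Day 1 and 96 after dosing. The reported change is 96 - 99 = -3 under 10.5, 96 - 97 = -1 under 6.4.1, and 96 - 96 = 0 under 6.2.1. Nothing changed after infusion, yet 10.5 shows a 3-point fall.

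**The case against.** The best defence is that 10.5 is one descriptive sentence that never calls its reference a baseline, while 1.2 and 6.4.1 speak to vital signs directly, so a careful programmer might use the last pre-dose value anyway. Prednisolone also starts on Day -1, so screening could have been meant as a steroid-free reference. Neither removes the point. The words in 10.5 are specific to this table, and no steroid rationale is stated. What stands is that the matter is small: the tables are descriptive and untested, the worst-case share falls to 14% by Day 180, and 6.4.1 and 6.2.1 differ by only about a day.

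A reader might infer more than the documents support:

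- **That a post-infusion value could become the baseline.** The wording that suggests this in SAP 10.4.3, "The baseline value will be the last measurement on or before the day of the infusion of study drug", governs laboratory tests, and the SAP schedule has no Day 1 laboratory draw. (Protocol Table 3 lists one, but Protocol 12.1.10 places the required Day -1 bloods before infusion.) The protocol's default in 14.3.1, "the baseline measurement is defined as the last non-missing measurement collected prior to or on the day of gene replacement therapy infusion", sits under efficacy, applies only where nothing else is specified, and gives way to the SAP under SAP 2. For vital signs with recorded times, 6.2.1 takes the last one before infusion. Day 1 weight is measured pre-dose.
- **That mean weight change is overstated by a definite amount.** The documents give no growth rate. If 0.4 to 0.8 kg per 30 days is assumed, the shift per patient runs from about 0.03 to 0.05 kg (2/30 of that gain) to 0.4 to 0.8 kg. The upper end applies to the mean only if every patient is screened on Day -30.
- **That a treatment effect is hidden or invented.** Without a comparator, these summaries do not estimate a treatment effect under any baseline.
- **That the PCS counts are distorted.** SAP 10.5 starts those counts at Day 1, and the criteria are kept outside the SAP, so this cannot be checked.

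**Conclusion.** The inconsistency is real and minor. SAP 10.5, taken as written, contradicts SAP 1.2, 6.2.1 and 6.4.1 and adds 2 to 30 pre-dose days to every vital-sign change. Depending on the screening day, these make up 67% to 97% of the interval at Day 2 and 2.2% to 25% at Day 90. No primary or secondary efficacy test is affected.

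This rests on three assumptions:

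- The first recorded value is the screening value. That is inferred from the schedule, but no other reading fits as well.
- Days are counted on the nominal protocol calendar. The Study Day formula in SAP 1.2 gives the day before dosing the value 0, which would make the span 3 to 31 days.
- The percentages are shares of elapsed time. They equal shares of the change itself only for a measure that moves at a constant rate.

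**What to change.** In SAP 10.5, replace the first-recorded-value reference with the SAP 6.2.1 baseline, stated as the last non-missing value before the start of infusion, by date and time. Align the Day 1 wording in 6.4.1 with the same rule so that Day 1 pre-dose values are used. The pre-dose span then falls to 0 days where a Day 1 pre-dose value exists; with 6.4.1 left as it is and read literally, about 1 day would remain. If change from screening is of interest, for example as a reference before steroids, show it as a labelled supplement with its reason.

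The cost is a wording change in two SAP sections and the matching table specification. No data collection, visit or sample size changes.
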